#### **Data Collection Methods**

#### 1. Quantitative data collection

Data will be collected on predetermined days on the postnatal areas of each participating site. Suitable days will be identified by the local lead at each site to fit with availability of study team members. Data will be collected by trained members of our research team from parents of participants, clinical records and healthcare professionals including nursery nurses and midwives.

The following data will be collected:

Table 1: All datapoints collected for Primary Objectives 1 and 2

Datapoint	Source	Collection timepoint
Demographic details and baseline	data	
Eligibility confirmation	Medical record and/or direct questioning of parent/carer	Enrollment
Date of birth (dd/mm/yyyy)	Medical record	Enrollment
Time of birth (hh:mm)	Medical record	Enrollment
Gestational age (weeks + days)	Medical record	Enrollment
Birthweight (g)	Medical record	Enrollment
Ethnicity of birthing parent (recorded)	Medical record	Enrollment
Ethnicity of birthing parent (reported)	Direct questioning of parent/carer	Enrollment
Ethnicity of 2nd biological parent (if known)	Direct questioning of parent/carer	Enrollment
Index of Multiple Deprivation (as calculated by postcode of birthing	Medical record	Enrollment

		1
parent)		
Need for translator	Direct questioning of parent/carer	Enrollment
Jaundice and skin tone assessmen	t	
Feeding method a	Direct questioning of parent/carer	Enrollment
Skin tone as per skin tone tool b	Skintone assessment by study team member	Enrollment
Indication for jaundice assessment c	Medical record and/or HCP that identified eligible participant	Enrollment
TcB measurement d	Medical record and/or HCP that identified eligible participant	Enrollment
Serum bilirubine	Medical record and/or HCP that identified eligible participant	Enrollment
Immediate management planf	Medical record	Enrollment
Retrospective		
Duration of admission	Medical record	14 days
Location of admission	Medical record	14 days
Treatment administered 	Medical record	14 days
Feeding at discharge a	Medical record	14 days
Investigation results h	Medical record	14 days
Has the participant been diagnosed with G6PD deficiency and/or haemolytic disease of the newborn (HDN)	Medical record	14 days

<sup>a Exclusively breastfeeding, Mixed feeding, Exclusively formula feeding

<sup>b 1, 2, 3 or 4 as per Maya-Enero et al.

<sup>c Visibly jaundiced (parent/carer noted), visibly jaundiced (HCP noted), risk factors, routine, unwell, incidental

<sup>dRole of staff member performing measurement, Value and units, Location on body, Brand and model of machine, Time of measurement, Date of measurement eRole of staff member performing measurement, Value and units, Value relative to treatment line (micromol/L above/below line), Type of SBR (blood gas, lab, spun bili),

Time of measurement, Date of measurement

fNo intervention, feeding plan implemented (e.g. not specified, breastfeeding support, top ups), repeat bilirubin assessment indicated at a later time point (with time point specified), commence single phototherapy, commence double phototherapy, admit to NICU

Received IVIG, received exchange transfusion

hWhich of the following investigations were performed and what were their results: DAT, G6PD, blood cultures, participant blood group, birthing parent's blood group.

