Our preliminary survey has also helped ensure that language used in the PIS is clear and easily understandable, for all levels of literacy. It will be professionally translated into the languages most relevant to the study population and local site translation services will be used to aid discussions around the opt-out consent process for quantitative data collection as well as consenting for the parent survey and focus groups/ semi-structured interviews.

The risk of data breach will be minimised by entering pseudonymised data into an encrypted data collection tool (REDCap) with data held within QMUL with our data Safehaven. Data entered here will not be linked to any participant-identifiable information. Parent survey responses will also be held in the encrypted NHS Microsoft 365 Forms platform and no patient identifiable data will be collected. Parent focus group/ semi-structured interview transcripts will be securely stored and only accessible to study teams for thematic analysis.

If the study enrolment happens as planned, there should be no delay in receipt of standard of care. However, should there be a misunderstanding between the midwifery and medical staff, there is a very small risk routine care would be delayed. This will therefore be highlighted very clearly in study team training to minimise this risk and ensure any clinical need is prioritised over study enrolment.

There is a risk that given the unblinded nature of the study, health care professional (HCP) perception of need for jaundice testing would be affected. We do not anticipate the number of jaundice tests at each site to increase due to participation in the study. However, we appreciate that the presence of an ongoing study may change healthcare worker behaviour, to minimise this the full details of the study will only be discussed with local study leads, who will not be the healthcare workers identifying patients for investigation for jaundice on data collection days.

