## 6.3. Primary endpoints

- Absolute value of first bilirubin measurement in neonates of different skin tones
- 2. Value of first bilirubin measurement relative to NICE phototherapy / exchange transfusion treatment lines in neonates of different skin tones
- 3. Age of neonates of different skin tones at first bilirubin measurement
- 4. Indication for bilirubin assessment in neonates of different skin tones

[Assessed through data collected by local teams during prospective data collection]

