#### Study processes during prospective data collection phase

Potentially eligible neonates will be identified by postnatal area healthcare professionals and REACH/BiliNEST local study team members will determine their eligibility. The research team at each site will consist of the local lead study team member and a number of additional data collectors who have undergone training, all of whom are paediatric resident doctors as part of the direct care team. These individuals will review whether or not these neonates meet the eligibility criteria, and approach the birthing parent to ask if they are happy to discuss a research study. The number of participants deemed ineligible and the reason for exclusion will be documented. The study process and opt-out consent model will be explained verbally, and patient information leaflets will be provided in English or in the most relevant language available.

Local data collectors will receive an SOP detailing the introductory conversation aims with parents / carers, in particular, to be clear that there will be no detrimental consequences to them or their child if they opt out. A filmed, scripted example of an introduction will be included, that uses sensitive, non-coercive language; the script of which has been vetted by our PPI group. In addition, all data collectors will have completed Good Clinical Practice training, which includes the principles of appropriately obtaining informed consent and will have attended a training session on study processes.

The data collected from the parent/carer is listed in Table 1. The only data collected from participant examination is skin tone / colour group. Neonates will undergo a visual inspection by local study team members within twelve hours of their first bilirubin measurement and then categorisation into one of the four skin colour groups. We recognise that babies may be naturally lighter or darker than those depicted in the skin tone tool groups. When this is the case, babies will be assigned to the group closest to their natural skin colour e.g. for a baby who has a skin colour darker than group 4, they will be included within group 4. All study team members will be trained in the use of the tool to ensure the use of acceptable language and to minimise inter-user variability.

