# 9. Study procedures

#### **Opt-out Consent (Primary Objectives and Secondary Objective 1):**

- An opt-out consent model will be used for the primary objectives. This means that all eligible participants will be enrolled unless either of the parents / carers actively opt out. However, agreement from one parent is sufficient if the second parent is not present.
- A verbal and written explanation of the study will be provided, explaining the study objectives, procedures, risks, and benefits alongside the opt-out consent model.
- The written information will be available in a range of languages appropriate to the local population for each site.
- If required, a professional translator will be used to translate all relevant information, either in person or telephonically.
- Parents will be given a minimum of 15 minutes to consider the information and to ask questions as required, before study data is collected. The PIS will contain details on how to contact the study team to opt-out at any later stage.
- If parents opt-out of inclusion in the study, there will be no impact on the routine care provided

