## **Screening and recruitment:**

- On data collection days, staff members carrying out jaundice assessments in relevant inpatient areas will be notified and asked to alert the research team when any neonates are undergoing their first TCB or SBR
- Standard clinical care will not be delayed for enrollment
- Identification of potential eligible babies will occur via a written identification table in postnatal areas. Outcomes, i.e. included or excluded, and reasons for exclusion will be noted in the infant's clinical record.
- The research team at each site will consist of the local lead and a number of additional data collectors who have undergone training. These individuals will review whether or not these neonates meet the eligibility criteria, and approach the birthing parent to discuss the study if eligible
- Study data will be collected in participants where all eligibility criteria are met

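### Table 1 lets the indication for testing, a primary endpoint, be coded with the bilirubin reading already known, because staff recall is an equal source and nothing need be written before the result

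*Protocol*

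**What the plan says.** Section 6.3 of the protocol lists as its fourth primary endpoint "Indication for bilirubin assessment in neonates of different skin tones". Table 1 in Section 8 collects the indication at enrolment and gives its source as "Medical record and/or HCP that identified eligible participant". The rows for the TcB and serum bilirubin values carry the same source and the same timepoint. The row for the immediate management plan, by contrast, names the medical record alone. The footnote offers six categories of indication: visible jaundice noted by a parent or carer, then "visibly jaundiced (HCP noted), risk factors, routine, unwell, incidental".

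On sequence, Section 9 has the assessing staff "asked to alert the research team when any neonates are undergoing their first TCB or SBR", and says that "Identification of potential eligible babies will occur via a written identification table in postnatal areas". Under the opt-out procedure, "Parents will be given a minimum of 15 minutes to consider the information" before study data are collected. Skin tone, also an enrolment item, is assessed "within twelve hours of their first bilirubin measurement" (Section 8).

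Section 10.2 names the indication as a possible mediator between skin tone and bilirubin, to be explored if time allows. Section 5.2 gives the premise that visual detection may work less well in darker skin.

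**The concern.** An indication is a statement about why a test was done, so it should be fixed before the result exists. Here it may be supplied afterwards by the person who did the test. An infant tested for a risk factor or as routine, who then reads high, can be remembered as having looked jaundiced. The categories overlap, so this recoding needs no bad faith.

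If recoding is equally common in all skin tones, it blurs the endpoint but creates no difference between tones. If it differs by tone, the distribution of indication by tone is biased. On the study's own premise a difference is plausible, since a high reading may be easier to reinterpret as visible jaundice where yellowing shows. Any mediation analysis using the indication would inherit the error. No later analysis can recover a reason that was not recorded before the reading.

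**Working it through.** The protocol gives no figure for this point, so there is nothing to reproduce. The check has two parts.

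**1. Does anything require the reason to be recorded before the reading?**

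- *Source and timepoint (Table 1):* the same for the indication and for the bilirubin values. The staff member asked for the reason can also be the one who supplies the result.
- *Order of events (Sections 8 and 9):* the alert comes while the first test is being done. The explanation and at least 15 minutes follow before study data are collected, and the skin tone assessment may come up to twelve hours after the measurement. Data collection is therefore at or after the test, and a TcB reading will usually be known.
- *Restricted study details (Section 5.3):* these are kept to local leads, "who will not be the healthcare workers identifying patients for investigation for jaundice on data collection days". That bears on who gets tested, not on when the reason is written.
- *Ward identification table (Section 9):* its columns are not listed, and it is not said to hold the indication.
- *Recruitment logs (Section 13.1):* contemporaneous with recruitment, not with the decision to test.

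None of these requires recording before the result, and none ranks the medical record above recall.

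**2. How large could the effect be? (illustration only)**

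Let v be the true share of visual indications, equal in both tones, and q the share of above-median non-visual tests recoded as visual. Half of the non-visual tests are taken to lie above the median. Then:

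recorded visual share = v + (1 − v) × 0.5 × q

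Assumed values, none of them from the protocol: v = 0.60, q = 0.2 to 0.4 in lighter infants and 0 to 0.1 in darker infants. The formula becomes 0.60 + 0.20 × q.

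| q lighter | q darker | share lighter | share darker | difference |
|---|---|---|---|---|
| 0.2 | 0.1 | 0.64 | 0.62 | 2 points |
| 0.2 | 0 | 0.64 | 0.60 | 4 points |
| 0.4 | 0.1 | 0.68 | 0.62 | 6 points |
| 0.4 | 0 | 0.68 | 0.60 | 8 points |

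The four corners span 2 to 8 percentage points with no true difference. With equal q the difference is zero, and if the two q values are swapped the sign reverses.

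For scale, Section 8 plans 560 infants, and the sample size section assumes 50% in tone 1 and 10% in tone 4, so 280 and 56. Near a 60% share, the standard error of the difference is √[0.6 × 0.4 × (1/280 + 1/56)] = 0.072, or about 7 points. The illustrated bias is about 0.3 to 1.1 standard errors for that contrast.

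The result moves with the assumptions. If recoding applies to all non-visual tests, the share is v + (1 − v) × r, where r is the recoded share. With v = 0.50 and r = 0.20 against 0.05, this gives 60.0% against 52.5%, or 7.5 points. With v = 0.70 and r = 0.10 against 0.05, it gives 73.0% against 71.5%, or 1.5 points. With v = 0.30 and r = 0.30 against 0.10, it gives 51% against 37%, or 14 points.

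**The case against.** The strongest reply is that little depends on this variable and that recall may be rare. The medical record is a named source and may hold a reason written before the test. Staff raise the alert while the test is under way, and a laboratory serum result may still be pending. Keeping full study details from identifying staff lessens any motive to recode. An infant with a risk factor who also looked yellow has two valid reasons, so choosing the second is not necessarily an error. The CRF and the SOP are not reproduced and may set a source order. All of this makes wholesale recoding less likely. None of it removes the route that Table 1 leaves open, and Table 1 itself puts the two sources on equal terms.

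Three stronger readings are tempting, and the documents do not support them.

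- A reader might infer that lighter infants will be over-recorded as visually detected. That direction is reasoned from the premise in Section 5.2 and is not documented. Staff who learn of a high reading in a darker infant might equally say that they had noticed.
- A reader might infer that recoding hides part of a true bilirubin excess among visually detected darker infants. Section 10.2 plans no bilirubin comparison within indication groups. Putting a µmol/L figure on it would need an assumed spread and equal means in visual and non-visual tests, which the protocol does not give.
- A reader might infer that the main result for Primary Objective 1 is biased. The model regresses bilirubin on skin tone and age, with deprivation and gestational age as possible additions. Indication is not among its named covariates.

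**Conclusion.** The point holds as a weakness in how one primary endpoint is captured. As written, the plan permits the indication to be coded with the bilirubin reading already known. If that happens unevenly by skin tone, the distribution of indication by tone is biased, and so is any exploratory mediation analysis. The mixed model for first bilirubin is not affected.

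On the main illustration the spurious difference is about 2 to 8 percentage points. That range rests wholly on the assumed 60% visual share and the assumed recoding rates, and equal recoding removes it. This is a cheap improvement, not an error that threatens the study.

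**What to change.** Have the person who decides on the test enter the indication on the ward identification table at that moment, before the reading is known; add a column if the table has none. In Table 1, replace the unranked pair of sources with an order: this entry first, the medical record second, staff recall last. Add one CRF field for the source used, so that results can be checked in infants whose indication was recorded before the reading.

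The cost is at most one column on a form already in use, one CRF field and a few seconds of ward staff time per test. Clinical care does not change.

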# 4. Summary and synopsis

Short title	BiliNEST
Methodology	Prospective multicentre observational study utilising the London REACH (Research Evaluation and Audit for Child Health) Network
Objectives / aims	We aim to investigate whether there are disparities in the jaundice assessments for neonates of different skin tones in London through the following objectives:  Primary Objectives:  1. To assess the level of first bilirubin measurement in neonates of different skin tones and determine whether neonates with darker skin tones are being assessed for jaundice once they have reached a higher bilirubin level, as compared to lighter skinned neonates.  2. To evaluate the agreement between TcB and SBR measurements in neonates of different skin tones.  Secondary Objectives:  1. To investigate immediate management of neonates of different skin tones undergoing assessment for jaundice: length of admission, investigations and receipt of interventions including phototherapy and exchange transfusion.  2. To review the range of existing local guidelines on management of neonatal jaundice, examining inter-guideline variation and variation from national clinical practice guidelines and the extent of guideline adherence.  3. To collate opinions and experiences from a diverse population of parents and carers regarding their understanding of neonatal jaundice and its management, the impact of skin tone and/or ethnicity on jaundice assessment in neonates and the acceptability of the neonatal skin tone tool.
Number of participants	Number of participants  A minimum of 560 participants (an estimated 28 participants from each site) will be recruited in order to reach an appropriate total sample size for the quantitative data sections as detailed in Section 10.
	Much fewer participants will be required for the qualitative data objective, a small group will be included from those in the quantitative section.
	Study population
Inclusion and exclusion criteria	Participants will be recruited for the primary objectives (quantitative) data collection if they fulfil the following criteria:
	Inclusion criteria:

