#### 6.2. Secondary objectives

- 1. To investigate immediate management of neonates of different skin tones undergoing assessment for jaundice; primarily length of admission and need for interventions including phototherapy and exchange transfusion.
- 2. To review the range of existing local guidelines relating to the management of neonates with jaundice, how these guidelines vary from each other and from

- national clinical practice guidelines (such as NICE Jaundice in newborn babies under 28 days Clinical guideline [CG98]) and the extent to which they are being adhered to.
- 3. To collate opinions and experiences from a diverse population of parents and carers regarding their understanding of jaundice in neonates and its management, the impact of skin tone and/or ethnicity on jaundice assessment in neonates and the acceptability of the neonatal skin tone tool.

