### 6.4. Secondary endpoints

- 1. Diagnostic methods used to assess jaundice in neonates of different skin tones
- 2. Immediate management of neonates following jaundice assessment

[Assessed through data collected by local teams during prospective data collection]

3. Number of clinical practice guidelines used and variance between guidelines

[Assessed through data collected in pre-study survey of local leads at each site]

- 4. Acceptability of a validated neonatal skin tone tool in a diverse population of parents and carers
- 5. Parent and carer understanding of neonatal jaundice
- 6. Parent and carer opinions and experiences of the impact of skin tone and/or ethnicity on jaundice assessment in neonates

[Assessed through data collected in parents/carer completed surveys and through focus groups and semi-structured interviews]

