Primary objective 1 will be using a linear mixed model, with skin tone and confounders as fixed effects and hospital as a random effect. The outcomes will be the coefficient difference between baseline skin tone and the other 3, with 95% CI.

Primary objective 2 will use the Bland-Altman to detect differences of measurement between skin tones, stratified by method of how the measurement for how serum bilirubin was taken. The mean of the differences will be provided with 95% CI, along with the IQR of difference with accompanying p-value. The rate of over/under-estimation will also be estimated between different skin tones. Bland-Altman plots will be reported as well as Specificity and sensitivity analyses using Receiver operating characteristic (ROC) curves.

Secondary Objective 1: Primary length of admission differences between skin tone will be compared using survival analysis of time to event data (Kaplan-Meier plot, Cox Proportional Hazards Model). The need for interventions including phototherapy and exchange transfusion will be done using generalised linear mixed models, with outcomes reported as Odds Ratios with 95% CI.

Age of infant at measurement is an important metric and shall be included as a fixed covariate in all models other than Bland-Altman (baseline model). Additionally, IMD and gestational age may be included as additional covariates (adjusted model). However, due to the complex relationship between skin colour and medical intervention, we run the risk of over-adjusting on covariates and inducing collider bias and/or mediators. For example, skin tone may affect what the indication for jaundice assessment was, and this in turn may affect the outcome of bilirubin and if there was a delay for treatment, making it a mediator. With sufficient time, this relationship may be explored to see if different skin tones are affected by how their jaundice is first indicated, which influences clinical guidelines if an association is found between skin tone and indication which in turn affects bilirubin levels.

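### Secondary Objective 1 promises receipt of phototherapy, but Table 1 records only the plan at enrolment, so later or undelivered phototherapy cannot be identified

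*Protocol*

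**What the plan says.** **Objective.** The synopsis (section 4) describes Secondary Objective 1 as the immediate management of neonates of different skin tones, covering "length of admission, investigations and receipt of interventions including phototherapy and exchange transfusion". Section 6.2 also refers to immediate management but words the content as "primarily length of admission and need for interventions including phototherapy and exchange transfusion". The matching endpoint in section 6.4 is "Immediate management of neonates following jaundice assessment".

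**Analysis.** Section 10.2 states: "The need for interventions including phototherapy and exchange transfusion will be done using generalised linear mixed models, with outcomes reported as Odds Ratios", with 95% confidence intervals. Phototherapy and exchange transfusion share one sentence and one model type.

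**Data.** Table 1 (section 8) has two relevant items:
- The immediate management plan, collected at enrolment. Footnote f lists its options, including no intervention, a repeat bilirubin at a later time, and "commence single phototherapy, commence double phototherapy, admit to NICU".
- Treatment administered, taken from the medical record at 14 days. Footnote g defines it as "Received IVIG, received exchange transfusion".

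Section 9 (study procedure) refers to Table 1 for the full list of data with sources and timepoints. Table 1 is titled for the two primary objectives, but it is the only quantitative data list and it holds the other Secondary Objective 1 items, such as duration of admission. Section 13.1 adds that management required may be entered after recruitment, without naming a field.

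**The concern.** The two interventions in one analysis sentence are measured in different ways. Exchange transfusion is recorded as given or not by 14 days; phototherapy is recorded only as an intention at the first assessment. Two kinds of baby then cannot be classified for receipt:
- a baby whose enrolment plan was no intervention or a repeat bilirubin and who started phototherapy later;
- a baby whose plan was phototherapy but who never received it.

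This matters because the study asks whether darker-skinned babies are first tested at higher bilirubin levels. If they are, the share of phototherapy decided at the first test, and so the share that the plan item misses, could differ by skin tone. Error that depends on the exposure can distort a comparison by exposure, and with no 14-day phototherapy field the analyst could neither detect nor correct it.

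**Working it through.** No stated figure of the protocol is at issue, so there is none to reproduce. The check traces the outcome through the document and then illustrates the possible effect.

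**1. Trace**

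| Step | Exchange transfusion | Phototherapy |
|---|---|---|
| Synopsis | receipt | receipt |
| Section 6.2 | need | need |
| Section 10.2 | mixed model, odds ratio | mixed model, odds ratio |
| Table 1, enrolment | not an option of the plan | option of the plan (footnote f) |
| Table 1, 14 days | received (footnote g) | no field |

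The chain is complete for exchange transfusion. For phototherapy it breaks at the 14-day step. No other table covers Secondary Objective 1.

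**2. Illustration of missed later starts (all rates assumed)**

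Let p be the true proportion receiving phototherapy by 14 days and m the share of those courses that start after the enrolment plan and are missed. Then

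- recorded proportion = p × (1 − m)
- odds = proportion / (1 − proportion)
- OR = odds (darker) / odds (lighter)

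Take p = 0.20 (lighter) and 0.30 (darker). True OR = (0.30/0.70)/(0.20/0.80) = 1.71.

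| Missed, lighter | Missed, darker | Recorded, lighter | Recorded, darker | Recorded OR |
|---|---|---|---|---|
| 10% | 10% | 0.18 | 0.27 | 1.68 |
| 30% | 30% | 0.14 | 0.21 | 1.63 |
| 50% | 50% | 0.10 | 0.15 | 1.59 |
| 10% | 30% | 0.18 | 0.21 | 1.21 |
| 20% | 50% | 0.16 | 0.15 | 0.93 |
| 30% | 10% | 0.14 | 0.27 | 2.27 |

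Equal loss pulls the odds ratio modestly towards 1. Unequal loss can shrink, reverse or inflate it.

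**3. A null scenario (also assumed)**

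Both groups have 30% phototherapy by 14 days, but it is decided at the first test in 15% of the lighter group and 25% of the darker group. True OR for receipt = 1.0. Recorded OR = (0.25/0.75)/(0.15/0.85) = 0.333/0.176 = 1.89.

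These are crude odds ratios. Section 10.2 puts age at measurement into all models other than Bland-Altman, and age is closely tied to early or late detection, so the modelled values could differ. Planned courses that were not given would add error of the opposite kind, which is not included here.

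**The case against.** The strongest reply is that the data item fits the endpoint. Sections 4 and 6.2 both introduce the objective as immediate management, section 6.4 names immediate management as the endpoint, and sections 6.2 and 10.2 speak of need; only the synopsis says receipt. For phototherapy decided at the first assessment, footnote f records what is wanted. Under that target, the 25% against 15% in the null scenario is a real difference and 1.89 is the right answer, not a biased one. This stands, and it limits the point to receipt and later starts. It does not remove the point: the synopsis does promise receipt, and the protocol already follows IVIG, exchange transfusion and admission to 14 days.

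A second reply is that section 13.1 lets management required be added later. That shows later management was foreseen, but the wording is permissive, defines no field and is not carried into Table 1, so it would not give a uniform outcome across sites. An analysis plan could not supply a variable that was never collected.

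Three stronger readings are tempting and are not supported:
- That later phototherapy is definitely counted as none. The protocol gives no coding rule; this follows only if the outcome is built from Table 1 as it stands.
- That the odds ratio is biased away from 1. That is one scenario. The table above shows movement in both directions, and the documents give no phototherapy rates or start times by skin tone.
- That TcB-SBR pairs are contaminated by samples taken after phototherapy. Babies enter at their first bilirubin assessment and each measurement is timed; the documents do not show that such pairs would enter.

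**Conclusion.** The inconsistency is real: the synopsis and the analysis section call for a phototherapy outcome that Table 1 can supply only as a plan at first assessment. As written, the study cannot identify phototherapy started later or planned but not given. This conclusion rests on the text alone, taking Table 1 as the full data list, as section 9 says.

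The effect on the odds ratio is unknown. The values of 0.93 to 2.27 against a true 1.71, and 1.89 against a true 1.0, rest wholly on assumed rates and on receipt by 14 days being the target. They show that the error could matter, not that it will.

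The point should be fixed but is not critical. It touches one component of one secondary objective, whose sample size section 10.1 leaves to the primary objectives. The primary objectives, length of admission and exchange transfusion are unaffected.

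**What to change.** **Preferred.** Extend the 14-day treatment item in Table 1 (footnote g) with phototherapy received: yes or no, date and time first started, single or double. Use this as the receipt outcome of Secondary Objective 1 in section 10.2. Keep the enrolment plan as a separate endpoint for immediate management, and align the wording of sections 4, 6.2 and 6.4 so that each outcome is named.

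**Alternative.** If receipt is not wanted, restrict sections 4, 6.2 and 10.2 to phototherapy planned at first assessment.

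**Cost.** The preferred change adds a few fields to the case report form and REDCap, within a record review already scheduled, plus a minor amendment. Babies already enrolled can be back-filled through the local linkage record (sections 13.2 and 13.3). Section 13.2 keeps that record only for the duration of the study, so the change should be made early. The alternative costs only wording. Both concern data collection and reporting only; neither alters clinical care.
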